#### **12.4.5 Progression-Free Survival**

PFS is defined as the duration of time from start of treatment to time of progression or death, whichever occurs first.

### **13.0 DATA AND SAFETY MONITORING**

In compliance with the Washington University Institutional Data and Safety Monitoring Plan, the Principal Investigator will provide a Data and Safety Monitoring (DSM) report to the Washington University Quality Assurance and Safety Monitoring Committee (QASMC) semi-annually beginning six months after accrual has opened (if at least five patients have been enrolled) or one year after accrual has opened (if fewer than five patients have been enrolled at the six-month mark).

During the phase I dose escalation, the Principal Investigator will review all patient data at least monthly (or before each dose-escalation if occurring sooner than monthly), and provide a semi-annual report to the Quality Assurance and Safety Monitoring Committee (QASMC). During the phase II, the Principal Investigator will review all patient data at least every six months, and provide a semi-annual report to the QASMC. This report will include:

- HRPO protocol number, protocol title, Principal Investigator name, data coordinator name, regulatory coordinator name, and statistician
- Date of initial HRPO approval, date of most recent consent HRPO approval/revision, date of HRPO expiration, date of most recent QA audit, study status, and phase of study
- History of study including summary of substantive amendments; summary of accrual suspensions including start/stop dates and reason; and summary of protocol exceptions, error, or breach of confidentiality including start/stop dates and reason

- Study-wide target accrual and study-wide actual accrual
- Protocol activation date
- Average rate of accrual observed in year 1, year 2, and subsequent years
- Expected accrual end date and accrual by cohort
- Objectives of protocol with supporting data and list the number of participants who have met each objective
- Measures of efficacy
- Early stopping rules with supporting data and list the number of participants who have met the early stopping rules
- Summary of toxicities separated by cohorts with the number of dose-limiting toxicities indicated
- Abstract submissions/publications
- Summary of any recent literature that may affect the safety or ethics of the study

The study principal investigator and Research Patient Coordinator will monitor for serious toxicities on an ongoing basis. Once the principal investigator or Research Patient Coordinator becomes aware of an adverse event, the AE will be reported to the HRPO and QASMC according to institutional guidelines.

## **14.0 STATISTICAL CONSIDERATIONS**

### **14.1 Sample Size**

In the phase I part of the study, a de-escalation 3+3 design is used to determine the recommended phase II dose of tosedostat when combined with capecitabine in patients with advanced or metastatic pancreatic adenocarcinoma. The minimal number of patients needed for the phase I part of the study is 6 patients assuming no DLT is observed in Dose Level 1. The maximal number of patients is 12 patients.

For the phase II part of the study, the primary endpoint of the study is to assess the progression-free survival (PFS) of the combination therapy. Based on historical data, the PFS of 2.0 months was observed with either 5-FU or capecitabine in the second-line setting, so a median PFS of 4 months for the combination regimen would be considered clinically meaningful for further development. With a sample size of 36 patients including 3-6 patients from the phase I portion, the study has power 0.80 to identify an increase of the median PFS (2.0 to 4.0 months) at a 0.05 significance level, assuming 12 months of accrual and 6 months of follow-up. We will consider this phase II part as a pilot study for the PFS as endpoint; therefore a sample size of 36 is adequate. We expect to enroll 3-4 patients per month; therefore it is feasible to recruit 36 patients within 1 year.

### **14.2 Data Analysis**

PFS and OS will be estimated by Kaplan-Meier product limit method. The progression-

free survival and overall survival probabilities at certain time points (e.g. 3 months, 6 months) will be presented as well. The overall response rate (ORR) and CA19-9 response will be characterized by summary statistics (frequency and proportion). The logistic regression model will be considered to explore the predictive molecular biomarkers, the prognostic biomarkers for treatment response, and to investigate the correlation between genetic alterations and response to treatment.

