## 2.3 Exploratory Objectives

1. To explore the predictive molecular biomarkers for treatment response in patients with advanced or metastatic pancreatic cancer being treated with tosedostat and capecitabine combination therapy.
2. To explore the prognostic biomarkers for patients with advanced or metastatic pancreatic cancer receiving tosedostat and capecitabine combination therapy.
3. To correlate genetic alterations with response to treatment with combination tosedostat and capecitabine in patients with advanced or metastatic pancreatic cancer.

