### **9.2.3 Evaluation of genetic alternations that potentially associated with treatment response**

Pancreatic cancer, as all human malignancies, is caused by genetic mutations. Mutations in *KRAS*, *P16*, *TP53* and *SMAD4* genes are common (1821). With the advent of improved sequencing techniques, the identification of several key genetic alterations has led to the development of targeted therapies, such as imatinib and numerous EGFR-targeted therapies (cetuximab, erlotinib). Identifying the key genetic alterations in pancreatic cancer may lead to a better understanding of carcinogenesis and the development of more effective therapies. It is also important to analyze the somatic mutations and correlate them with treatment response and overall survival as there may be certain genetic alterations that prove to be more chemosensitive to certain drugs than others.

The Genomics and Pathology Service at Washington University (GPS@WU) offers next-generation sequencing of tumor somatic mutations in 42 oncogenes, tumor suppressors, and other cancer genes. The rationale for performing next generation sequencing is to identify the key genetic alterations in each patient's tumor. This information can then be used to compare patients' clinical information to see if there is a correlation between response rates, overall survival, and specific genetic mutations.

Next generation sequencing is performed on all coding regions of ABL1, AKT1, ALK, APC, ASXL1, ATM, BRAF, CEBPA, CTNNB1, DNMT3A, ERBB2, EGFR, ESR1, FGFR4, FLT3, IDH1, IDH2, JAK2, KIT, KRAS, MAPK1(ERK), MAP2K2(MEK), MET, KMT2A(MLL), MPL, MYC, MYD88, NOTCH1, NPM1, NRAS, PDGFRA, PIK3CA, PTEN, PTPN11, RB1, RET, RUNX1, STK11, TET2, TP53, VHL and WT1 to detect single nucleotide variants and small insertions and deletions; selected introns of ALK and KMT2A(MLL) to

detect rearrangements. Next generation sequencing will be performed on initial tumor biopsies.

A GPS requisition form is obtained and completed from the Washington University Genomics and Pathology Services

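### Section 14.2 relates biomarkers only to treatment response, so the prognostic objective and the mutation–survival comparison described in 9.2.3 have no planned analysis

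*Combined protocol and SAP*

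**What the plan says.** Section 2.3 sets three exploratory objectives.

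- Objective 1: "To explore the predictive molecular biomarkers for treatment response".
- Objective 2: "To explore the prognostic biomarkers for patients with advanced or metastatic pancreatic cancer receiving tosedostat and capecitabine combination therapy". It names no outcome.
- Objective 3 relates genetic alterations to response.

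Section 9.2.3 goes further than objective 3. It calls it important to "analyze the somatic mutations and correlate them with treatment response and overall survival", and says the sequencing results can be used to "see if there is a correlation between response rates, overall survival, and specific genetic mutations". It names OS, not PFS.

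Section 14.2 covers all of this with one sentence. It begins "The logistic regression model will be considered to explore the predictive molecular biomarkers, the prognostic biomarkers for treatment response" and ends "to investigate the correlation between genetic alterations and response to treatment". For the time-to-event outcomes it says "PFS and OS will be estimated by Kaplan-Meier product limit method", with probabilities at time points such as 3 and 6 months. Nothing in 14.2 examines PFS or OS by marker.

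**The concern.** A prognostic marker is one that carries information about the course of the disease, which in this setting is mainly survival and time to progression. The protocol uses the term that way: section 1.4 supports the trial with a report that APN/CD13 expression, found in about half of resected pancreatic tumours, went with shorter overall survival and was an independent prognostic factor. Section 9.2.4 plans to stain for APN/CD13. Under 14.2 that marker would be examined against response alone.

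Two things are at stake. An analysis the protocol describes would have no prespecified method, so it would be dropped or improvised after the data are seen. And the one outcome that does have a model is likely to have very few events, while the PFS and OS data the trial collects anyway would add nothing to the biomarker work.

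**Working it through.** **Plan's own figure.** There is none to reproduce: the plan gives no response rate, responder count or biomarker power for this regimen. The power of 0.80 in 14.1 concerns PFS in the whole group, and nothing below uses it.

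**Stated aim against planned analysis.**

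| Stated aim | Outcome named | Analysis in 14.2 |
|---|---|---|
| Objective 1, predictive markers | Response | Logistic model |
| Objective 2, prognostic markers | None | Logistic model on response only |
| Objective 3, genetic alterations | Response | Logistic model |
| 9.2.3, mutations | Response and OS | Response only; nothing for OS |

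Objectives 1 and 3 are matched. The gaps are objective 2 and the OS half of 9.2.3.

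**Responders.** Inputs: n = 36 (14.1) and an assumed ORR. Expected responders = 36 × ORR.

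- 5%: 1.8
- 10%: 3.6
- 15%: 5.4
- The only ORRs in the documents (1.2; first-line, other regimens) run from 7% to 31.6%, giving 2.5 to 11.4.

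**What a response analysis can show.** Two-sided Fisher exact tests, 36 patients:

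- 4 responders, marker split 18/18, all 4 on one side: p = 0.104. No split reaches 0.05.
- 5 responders, 18/18, all 5 on one side: p = 0.045.
- 4 responders, marker split 9/27: p = 0.041 with 3 of the 4 in the smaller group, p = 0.002 with all 4.

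**Separation.** If all R responders share one marker status, the ordinary logistic estimate is infinite. With no true effect and m marker-positive patients, the chance is [C(m,R) + C(36−m,R)] / C(36,R).

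| Responders | 18/18 | 9/27 |
|---|---|---|
| 2 | 0.49 | 0.61 |
| 3 | 0.23 | 0.42 |
| 4 | 0.10 | 0.30 |
| 5 | 0.05 | 0.21 |

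**Events for a survival analysis.** Assume exponential times and uniform accrual over A = 12 months with F = 6 months' follow-up (14.1). With λ = ln 2 / median:

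events = 36 × {1 − [exp(−λF) − exp(−λ(A+F))] / (λA)}

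- PFS, median 4 months (λ = 0.1733): 36 × {1 − (0.3536 − 0.0442)/2.079} = 30.6.
- PFS, median 2 months (λ = 0.3466): 36 × {1 − (0.1250 − 0.0020)/4.159} = 34.9.
- OS, assumed medians 6.1 and 3.3 months (the extremes of the second-line treatment-arm figures in 1.3 from the two trials with a fluoropyrimidine control): 26.1 and 32.3.

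**Smallest detectable hazard ratio.** For one binary marker of prevalence q, two-sided 0.05 and 80% power: HR = exp[(1.960 + 0.842) / √(events × q(1−q))]. For example, 30.6 events at q = 0.5 give exp(2.802/2.77) = 2.75.

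| Outcome and events | q = 0.5 | q = 0.25 |
|---|---|---|
| PFS, 34.9 | 2.58 | 2.99 |
| PFS, 30.6 | 2.75 | 3.22 |
| OS, 32.3 | 2.68 | 3.12 |
| OS, 26.1 | 3.00 | 3.55 |

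Power for HR 2 on PFS at q = 0.5 is only 0.48 to 0.54. All these figures assume marker results for all 36 patients. The study calendar asks for archival tissue only if available, so real numbers may be lower.

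**The case against.** The strongest defence is one of scale. These are exploratory objectives in a part of the trial that 14.1 calls a pilot. The logistic model only will be considered, so other analyses are not excluded, and no significance level is set for biomarkers. No primary or secondary endpoint, sample size or safety matter depends on it. All of that stands, and it limits how much weight the point can bear. It does not close the gap: where 9.2.3 names OS and 14.2 offers no method, leaving other methods possible is not the same as planning one.

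It is also fair to say that Cox regression is no rescue. It needs a hazard ratio near 2.6 or above even for a common marker with complete tissue, and cannot carry a 42-gene screen. That stands too.

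Several stronger readings are tempting but unsupported.

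- **The response model cannot work.** With a 9/27 marker, 4 responders can give p = 0.041, and with 5 responders a balanced marker can reach 0.045. Very imprecise is the supportable description.
- **The plan expects about four responders.** It states no ORR. Four would need an assumed 11% (4/36). Nor does 14.2 tie treatment response to RECIST CR or PR, and a wider definition would change the count.
- **PFS and OS go unused, or 9.2.3 promises PFS.** Both outcomes get Kaplan-Meier estimates; they are unused only for biomarkers. Section 9.2.3 names OS alone.
- **The response screen yields 42 × 0.05 = 2.1 chance hits.** With so few responders the exact test falls well short of its nominal size. At an assumed 10% ORR its true size is about 0.009 for an 18/18 marker and 0.017 for 9/27, or 0.4 to 0.7 of 42. The figure 2.1 fits an unadjusted Cox screen better.
- **A hazard ratio and an odds ratio of the same value allow a direct power comparison.** They are different scales and not equal effects; event counts are the safer comparison.
- **Any hit would be wrongly called predictive.** The text says only that markers will be explored.

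**Conclusion.** The point holds as a mismatch between stated aims and planned analysis. Section 14.2 has no survival analysis by marker, although 9.2.3 intends one for OS and objective 2 concerns prognosis. This conclusion does not depend on any assumed response rate.

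The size of the secondary problem does. At assumed ORRs of 5% to 15% the response model would rest on about 2 to 5 responders, and about 11 at the highest first-line rate quoted. PFS would supply about 31 to 35 events and OS about 26 to 32, under exponential times, 12 + 6 months and complete tissue. That is a real gain in information for one or two prespecified markers, but enough only for large effects. Neither model can separate a predictive from a prognostic marker, because there is no comparison arm.

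The correction is worth making because it is cheap and makes 14.2 deliver what the protocol describes. It does not affect the trial's main conclusions.

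**What to change.** In section 14.2:

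1. Analyse prognostic biomarkers and genetic alterations against OS (as 9.2.3 intends) and PFS by Cox regression, with Kaplan-Meier curves by marker. Restrict this to a small number of markers named in advance, such as APN/CD13.
2. Keep response as a further outcome, define it, and use exact or Firth-penalised logistic regression, since separation is a real risk with so few responders.
3. Label the 42-gene screen hypothesis-generating. A false-discovery adjustment is optional at this stage.
4. State the limits: only large hazard ratios are detectable with 80% power (on PFS, about 2.6 to 2.75 at 50% prevalence and 3.0 to 3.2 at 25%); numbers fall if archival tissue is missing; and a single-arm trial cannot tell predictive from prognostic markers.

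The cost is a few sentences of plan text and a little more analysis, with no new patients or data. The downside is that biomarker claims will have to be more cautious.

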### **14.3 Interim Analysis**

After 10 evaluable patients have enrolled to the phase II portion of the study, an interim analysis will be conducted to look at response to date to assess for continuation of the study.

## APPENDIX A: ECOG Performance Status Scale

| Grade | Description                                                                                                                                                                           |
|-------|---------------------------------------------------------------------------------------------------------------------------------------------------------------------------------------|
| 0     | Normal activity. Fully active, able to carry on all pre-disease performance without restriction.                                                                                      |
| 1     | Symptoms, but ambulatory. Restricted in physically strenuous activity, but ambulatory and able to carry out work of a light or sedentary nature (e.g., light housework, office work). |
| 2     | In bed <50% of the time. Ambulatory and capable of all self-care, but unable to carry out any work activities. Up and about more than 50% of waking hours.                            |
| 3     | In bed >50% of the time. Capable of only limited self-care, confined to bed or chair more than 50% of waking hours.                                                                   |
| 4     | 100% bedridden. Completely disabled. Cannot carry on any self-care. Totally confined to bed or chair.                                                                                 |
| 5     | Dead.                                                                                                                                                                                 |

## APPENDIX B: PATIENT'S MEDICATION DIARY

Today's Date: \_\_\_\_\_ Cycle: \_\_\_\_\_ Patient Name: \_\_\_\_\_ Study ID#: \_\_\_\_\_

**INSTRUCTIONS TO THE PATIENT:**

1. Take \_\_\_\_\_mg ( \_\_\_\_capsules) of tosedostat daily, for 21 days, in the morning after food at approximately the same time each day. Take it with a glass of water. Swallow the capsules whole and do not chew the capsules.
2. Take \_\_\_\_\_mg in the AM ( \_\_\_\_tablets) and \_\_\_\_\_mg in the PM ( \_\_\_\_tablets) of capecitabine twice daily, for 14 days, after food at approximately the same times each day. Take it with a glass of water. Swallow the tablets whole and do not chew the tablets.
3. Record the date, the number of capsules and tablets taken, and when you took them.
4. If you forget to take any doses within 6 hours of the usual time, then do not take that dose. Restart at the next time you would normally take a dose.
5. If you notice any side effects, please record them in the comments section. Record the time if you should vomit.
6. Please return the forms to your physician or your study coordinator when you go to your next appointment. Please bring your unused study medications and/or empty bottles with you to each clinic visit so that a pill count can be done.

| Day | Date | Tosedostat |               | Capecitabine AM |              | Capecitabine PM |              | Comments |
|-----|------|------------|---------------|-----------------|--------------|-----------------|--------------|----------|
|     |      | Time       | # of capsules | Time            | # of tablets | Time            | # of tablets |          |
| 1   |      |            |               |                 |              |                 |              |          |
| 2   |      |            |               |                 |              |                 |              |          |
| 3   |      |            |               |                 |              |                 |              |          |
| 4   |      |            |               |                 |              |                 |              |          |
| 5   |      |            |               |                 |              |                 |              |          |
| 6   |      |            |               |                 |              |                 |              |          |
| 7   |      |            |               |                 |              |                 |              |          |
| 8   |      |            |               |                 |              |                 |              |          |
| 9   |      |            |               |                 |              |                 |              |          |
| 10  |      |            |               |                 |              |                 |              |          |
| 11  |      |            |               |                 |              |                 |              |          |
| 12  |      |            |               |                 |              |                 |              |          |
| 13  |      |            |               |                 |              |                 |              |          |
| 14  |      |            |               |                 |              |                 |              |          |
| 15  |      |            |               |                 |              |                 |              |          |
| 16  |      |            |               |                 |              |                 |              |          |
| 17  |      |            |               |                 |              |                 |              |          |
| 18  |      |            |               |                 |              |                 |              |          |
| 19  |      |            |               |                 |              |                 |              |          |
| 20  |      |            |               |                 |              |                 |              |          |
| 21  |      |            |               |                 |              |                 |              |          |

**DO NOT TAKE CAPECITABINE  
BEYOND DAY 14**

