### **5.2 Agent Administration**

Tosedostat is an oral drug which will be taken on an outpatient basis daily on a 21-day cycle. Patients should take tosedostat at approximately the same time every day (preferably morning) with a glass of water after food. If a patient misses a dose by more than 6 hours, the patient should be instructed not to take or make up that dose and to resume dosing with the next scheduled dose. Patients will be instructed to bring all unused drug and their medication diary (Appendix B) to each study visit for assessment of compliance. Dosing of tosedostat during phase I will be as described in Section 5.4. Dosing of tosedostat during phase II will be the dose determined during phase I.

Capecitabine is an oral drug which will be taken on an outpatient basis at a dose of 1000 mg/m^2 twice a day on Days 1 through 14 of a 21-day cycle. The tablets are to be swallowed with water and taken 30 minutes after the end of a meal. If the patient vomits or misses a dose by more than 2 hours, s/he must not take the missed dose and must not double the next dose. Instead, s/he should continue with the dosing as scheduled.

Patients will be instructed to bring all unused tablets and medication diary (Appendix B) to each study visit for assessment of compliance.

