### **8.2.7 Administration**

Capecitabine is an oral drug to be taken twice daily within 30 minutes after the end of a meal.

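### The patient diary applies one 6-hour missed-dose limit to both drugs, but Section 5.2 sets 2 hours for capecitabine

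*Combined protocol and SAP*

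**What the plan says.** Section 5.2 (Agent Administration) treats the two drugs separately. For tosedostat the limit is introduced by "If a patient misses a dose by more than 6 hours"; such a dose is neither taken nor made up. For capecitabine the limit is shorter: "If the patient vomits or misses a dose by more than 2 hours", then "s/he must not take the missed dose and must not double the next dose".

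The patient's medication diary in Appendix B covers both drugs. Item 1 is for tosedostat. Item 2 instructs the patient on a dose "of capecitabine twice daily, for 14 days, after food at approximately the same times each day". The recording grid has separate columns for tosedostat, morning capecitabine and evening capecitabine. Item 4 is the only missed-dose rule on the form, and it names no drug. It opens "If you forget to take any doses within 6 hours of the usual time" and tells the patient to skip that dose. It continues "Restart at the next time you would normally take a dose".

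Section 8.2.7 adds only this: "Capecitabine is an oral drug to be taken twice daily within 30 minutes after the end of a meal". It states no missed-dose limit.

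**The concern.** The protocol body and the sheet the patient uses at home give different rules for the same event. Both drugs are taken as an outpatient, so when a capecitabine dose is late the written instruction at hand is the diary. A patient who follows it can take a dose that Section 5.2 says must be skipped. On a fixed schedule, that dose also falls closer to the next one than it would at the Section 5.2 limit.

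Section 5.2 also makes the diary a tool for assessing compliance, and the grid records the time of each dose. A patient who obeys item 4 can thus document a departure from Section 5.2, and staff have two standards by which to judge it. Section 5.8 lists serious non-compliance as a reason to stop treatment. One late dose need not meet that criterion, but the standard should not depend on which page is read.

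**Working it through.** The plan states no figure to reproduce, so the check sets the texts side by side and then does simple arithmetic on the limits.

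**Inputs**
- Tosedostat limit, Section 5.2: 6 hours.
- Capecitabine limit, Section 5.2: 2 hours.
- Limit in Appendix B, item 4, no drug named: 6 hours.
- Capecitabine schedule, Section 5.2: twice daily on Days 1 to 14 of a 21-day cycle.

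**Step 1: does item 4 cover capecitabine?** Yes. It refers to doses without restriction, follows instructions for both drugs, and sits above a grid with columns for both. Nothing on the form limits it to tosedostat, and no 2-hour rule appears there.

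**Step 2: compare the rules for a late capecitabine dose.**

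| Lateness | Section 5.2 | Diary item 4 | Agree? |
|---|---|---|---|
| Up to 2 h | No bar on taking it | Skip rule not triggered | Yes |
| More than 2 h, up to 6 h | Must not be taken | Skip rule not triggered; implies it may be taken | **No** |
| More than 6 h | Must not be taken, next dose not doubled | Skip, resume at the next usual time | Yes |

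In the last row, the diary's instruction to resume at the next usual time largely covers the rule against doubling. For tosedostat the diary and Section 5.2 agree throughout, since both use 6 hours.

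**Step 3: look for text that reconciles the two.** Section 8.2.7 covers twice-daily dosing after a meal and is silent on missed doses. No other section gives a capecitabine limit.

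**Step 4: size of the conflict.**
- Disputed span per capecitabine dose: 6 − 2 = 4 hours.
- Doses to which it can apply: 2 per day × 14 days = 28 per cycle.

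**Step 5: time left to the next dose.** The documents give no interval between the morning and evening doses, so 8, 10 and 12 hours are assumed. The evening-to-morning interval is 24 minus that value. Time to the next dose = interval − lateness.

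| Assumed AM-to-PM interval | AM dose 2 h late (5.2 limit) | AM dose 6 h late (diary limit) | PM-to-AM interval | PM dose 2 h late (5.2 limit) | PM dose 6 h late (diary limit) |
|---|---|---|---|---|---|
| 8 h | 8 − 2 = 6 h | 8 − 6 = 2 h | 24 − 8 = 16 h | 16 − 2 = 14 h | 16 − 6 = 10 h |
| 10 h | 10 − 2 = 8 h | 10 − 6 = 4 h | 24 − 10 = 14 h | 14 − 2 = 12 h | 14 − 6 = 8 h |
| 12 h | 12 − 2 = 10 h | 12 − 6 = 6 h | 24 − 12 = 12 h | 12 − 2 = 10 h | 12 − 6 = 6 h |

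On any fixed schedule the diary limit brings the late dose 4 hours closer to the next one than the Section 5.2 limit does.

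**The case against.** The mismatch itself is hard to dispute, so the case on the other side is that it matters little.

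- **The conflict rests on an implication.** Item 4 only forbids doses beyond 6 hours. It never tells the patient to take one that is 2 to 6 hours late, and item 2 already asks for consistent dosing times. This is correct, but a patient given a 6-hour cutoff for skipping will naturally read an earlier dose as allowed.
- **Late dosing is visible to staff.** Dose times are recorded and the diary is reviewed at each visit, so a pattern could be found and corrected. That stands as mitigation, but it works after the dose has been taken.
- **Section 5.2 limits lateness and sets no minimum gap between doses.** This stands. A 6-hour gap can arise under Section 5.2 on an 8-hour schedule (8 − 2) and under the diary on a 12-hour schedule (12 − 6). The gaps can be compared only within one fixed schedule, where the diary's is the shorter.
- **The gap figures depend on assumed intervals.** This also stands. The 2-hour gap needs the shortest assumed interval and the greatest lateness of a morning dose. On that same schedule an evening dose 6 hours late still leaves 10 hours, more than the ordinary 8-hour daytime gap. Only the 4-hour span comes from the documents.
- **No statistical quantity is affected.** Agreed. This limits how serious the point is, but it does not remove the contradiction in a patient-facing dosing instruction.

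**Conclusion.** The inconsistency is real and sits in current text. For capecitabine doses more than 2 and up to 6 hours late, Appendix B item 4 implies that the patient may take a dose that Section 5.2 prohibits. The 4-hour span and the 28 scheduled doses per cycle follow directly from the documents. The time left to the next dose rests on the assumed 8, 10 or 12-hour daytime interval, and how often doses are this late is unknown.

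The consequence is limited. The late dose is one already prescribed for that day, no harm is demonstrated, and no effect on DLT counts, sample size, power or the analysis is shown. The text should be corrected because a compliant patient is led into a protocol departure, and the correction is easy.

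**What to change.** Split diary item 4 by drug, for example:

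- *Tosedostat: when a dose is over 6 hours late, leave it out and take the following dose at its normal time.*
- *Capecitabine: when a dose is over 2 hours late, leave it out and take the following dose at its normal time. Do not double it.*

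If the sponsor in fact wants 6 hours for both drugs, leave the diary limit and amend the capecitabine limit in Section 5.2 instead.

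Optionally, the capecitabine line could also carry the Section 5.2 instruction on vomited doses. The diary now asks only that the time of vomiting be recorded. That is a separate omission, convenient to repair in the same edit.

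The cost is a one-line change to the diary or to Section 5.2, plus IRB approval of the revised diary.
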